9.9 Subgroup and Other Analyses and Summaries

Several subgroups of interest have been identified for further exploration in relation to the effect on NOSE Scale scores and responder proportions:

- valve collapse mechanism (dynamic, static, mixture)
- prior septoplasty or turbinate surgery
- presence/absence of septal deviation
- presence/absence of enlarged turbinates.

Other areas of interest include:

- Characteristics of treatment nonresponders.
- Substudy of endoscopic nasal assessment images of participants identified with septal deviation. The study will examine the feasibility of grading the degree of septal deviation and assess the potential for correlation with NOSE Scale scores.

9.10 Safety Analysis

All adverse events (AE) will be analyzed for all participants. Adverse events are coded using a custom Aerin Medical dictionary so that adverse events may be categorized for analysis at an appropriate level of detail. Listings will be provided to detail individual events. The number of participants, number of AEs, and the proportion of participants reporting each AE will be summarized. Multiple occurrences of the same AE for a participant will be noted but only counted once for reporting of AE incidence. Seriousness and severity of AEs and their relationship to the device and procedure will be summarized. A time course of adverse events will be presented. Any unanticipated adverse device experiences or adverse events that occur at an unexpectedly high incidence rate will receive detailed analyses. Narratives will be presented for all deaths, serious adverse events, unexpected adverse device experiences, and participants withdrawn due to an adverse event.

Appendix A - Quality of Life Assessment

Compared to before I had the Aerin Medical Nasal procedure

	No Problem (0)	Very Mild Problem (1)	Mild or Slight Problem (2)	Moderate Problem (3)	Severe Problem (4)	Problem as bad as it can be (5)
1. Nasal obstruction						
2. Need to blow nose						
3. Sneezing						
4. Runny nose						
5. Cough						
6. Post-nasal discharge						
7. Thick nasal discharge						
8. Decreased sense of smell or taste						
9. Difficulty falling asleep						
10. Wake up at night						
11. Lack of a good night's sleep						
12. Wake up tired						
13. Fatigue						
14. Reduced productivity						
15. Reduced concentration						
16. Frustrated/restless/irritable						
17. Sad						
18. Embarrassed						
19. Snoring						
20. Mouth breathing during exercise						
21. Reduced sports or exercise tolerance						
22. Shortness of breath during experience						
23. Headache						
24. Nasal Congestion						

Statistical Analysis Plan TP900 (AERWAY)

Compared to the time prior to when you had the procedure, how often have you used each of the following products to help you with nasal congestion/difficulty breathing through your nose?

		Much less frequently	Less frequently	About the same	More Frequently	Much More Frequently
1.	Oral medications (antihistamines, oral decongestants)					
2.	Nasal sprays (nasal steroids, inhaled decongestants)					
3.	Nasal breathing strips (for example, BreatheRight® Strips)					

Rate Your Satisfaction:

1. How satisfied are you with the outcome (symptom relief) of your Vivaer Treatment (1-10)

(1 being my symptoms have no effect on my daily activity)

1 2 3 4 5 6 7 8 9 10

(10 being symptoms which completely prevent me from my daily activity)

2. Would you recommend the treatment to a friend or relative who suffered from the same nasal symptoms you had?

Yes No

3. If your symptoms were to come back would you chose to undergo the same procedure again?

Yes No

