4 STUDY OBJECTIVES AND ENDPOINTS

The primary objective of this study is to continue to evaluate the effectiveness of the Vivaer ARC Stylus for treating the nasal valve area to improve symptoms in those diagnosed with NAO. Effectiveness is assessed through several outcome measures and endpoints as described in Table 1. Outcome measures are further described in Section 8.

Statistical Analysis Plan TP900 (AERWAY)

Table 1. Objectives and endpoints.

Objective	Outcome measures and Endpoints
Evaluate effectiveness through symptom improvement.	
Nasal Obstruction Symptom Evaluation (NOSE) Scale score:
 
 • Mean and mean change from baseline at the 3-, 6-, 12-, 24-, and 36-month follow-up evaluations. • Distribution of NOSE Scale score severity categories (mild, moderate, severe, extreme) at the 3-, 6-, 12-, 24-, and 36-month follow-up evaluations. • Mean, change from baseline in mean, and response distribution of the 5 components of the NOSE Scale score (nasal congestion, nasal blockage, trouble breathing, trouble sleeping, and getting enough air during exercise) at the 3-, 6-, 12-, 24-, and 36-month follow-up evaluations. • Proportion of responders based on improvement in NOSE Scale score at the 3-, 6-, 12-, 24-, and 36-month follow-up evaluations.
Evaluate effectiveness through participant quality of life (QoL) questionnaire feedback.	
QoL questionnaire
 
 • Item response distributions and means where appropriate, at the 3-, 6-, 12-, 24-, and 36-month follow-up evaluations.
Evaluate safety through the safety profile.	
Adverse events
 
 • Frequency of device-related and procedure-related serious adverse events through the 3-month evaluation • Incidence (type, severity, relatedness) of adverse events overall and by follow-up interval.
Evaluate Other Exploratory Outcome Measures	
Nasal Assessment
 
 • Item response distributions prior to the procedure, immediately after the procedure, and at 3 months after the procedure. 
Visual analog scale (VAS) for pain
 
 • VAS pain score assessed at 3 months. 
Medications
 
Updates to current medications or any new or changed medications at the 3-, 6-, 12-, 24-, and 36-month follow-up evaluations.

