8.4 Participant Quality of Life Assessment

The QoL questionnaire consists of 4 parts (Appendix A). The first part has 24 items and asks the participant to rate how much of a problem various symptoms and potential effects of their nasal obstruction present to their quality of life at the time of taking the survey relative to the time prior to having the Vivaer procedure. A 6-point ordered rating scale is used with descriptors:

- No Problem (0)
- Very Mild Problem (1)
- Mild or Slight Problem (2)
- Moderate Problem (3)
- Severe Problem (4)
- Problem as bad as it can be (5).

The second part has 3 questions related to frequency of use of medical products for nasal obstruction symptom relief now compared to before the procedure. Responses are on a 5-point ordered rating scale with descriptors:

- Much less frequently
- Less frequently
- About the same
- More frequently
- Much more frequently.

There is also a response of not applicable if a product was not being used prior to the procedure.

Statistical Analysis Plan TP900 (AERWAY)

The third part has 3 questions. The first is a rating on a 10-point scale of satisfaction with symptom relief following the procedure where 1 represents symptoms have no effect on daily activity and 10 being symptoms completely prevent daily activity. The second question asks if the procedure would be recommended to a friend with similar symptoms (yes or no) and the third question asks if symptoms returned would you undergo the procedure again (yes/no).

The fourth section requests information on general health, including undergoing additional nasal surgery, significant changes in health, and changes to medication regimen.

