9.8 Outcome Measures Analyses

Data collected at postprocedure evaluation time points conducted after a participant received additional ENT procedures outside of the study protocol will be excluded

Statistical Analysis Plan TP900 (AERWAY)

from analysis of efficacy outcomes measures as these additional procedures would likely confound the effect of the original Vivaer treatment. For example, a participant who received a septoplasty after the 12-month evaluation will have any efficacy outcome measures that were collected after the septoplasty (24 months and 36 months) excluded from the analysis. Results after receiving additional treatments may be summarized separately.

Nasal Assessment - The visual physical and endoscopic assessment factors summarized to include frequency and percentage of responses in each category for each component of the nasal assessment at baseline, just prior to procedure, immediately after procedure, and 3 months after the procedure.

NOSE Scale score - Categorical responses and scores on the NOSE Scale and its individual components will be subject to multiple summary methods and analyses including the:

- Mean and mean change from baseline at the 3-, 6-, 12-, 24-, and 36-month follow-up evaluations.
- Distribution of NOSE Scale score severity categories (mild, moderate, severe, extreme) at the 3-, 6-, 12-, 24-, and 36-month follow-up evaluations displayed as number and percent.
- Mean, change from baseline in mean, and response distribution of the 5 components of the NOSE Scale score (nasal congestion, nasal blockage, trouble breathing, trouble sleeping, and getting enough air during exercise) at the 3-, 6-, 12-, 24-, and 36-month follow-up evaluations.
- Proportion (%) of responders based on improvement in NOSE Scale score at the 3-, 6-, 12-, 24-, and 36-month follow-up evaluations be displayed as number and percent.

VAS for pain - Summary will include mean (median) VAS pain scores assessed postprocedure and at 3 months.

Participant QoL Questionnaire – Responses to questionnaire items will be summarized by response category (frequency and percent) and by mean (median) response where appropriate at the 3-, 6-, 12-, 24-, and 36-month follow-up evaluations.

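### The 10-point QoL item asks for satisfaction but is anchored on symptom interference, so what a score measures, and which end is good, is ambiguous

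*SAP*

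**What the plan says.** The item opens the satisfaction block of the questionnaire in SAP Appendix A. Its stem reads "How satisfied are you with the outcome (symptom relief) of your Vivaer Treatment (1-10". The two ends of the response line are labelled "1 being my symptoms have no effect on my daily activity" and "10 being symptoms which completely prevent me from my daily activity".

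SAP 8.4 describes the same item in one sentence that joins both ideas: "The first is a rating on a 10-point scale of satisfaction with symptom relief following the procedure where 1 represents symptoms have no effect". The rest of that sentence repeats the interference anchors, with 10 at the opposite extreme.

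On analysis, the QoL row of SAP Table 1 lists "Item response distributions and means where appropriate" at 3, 6, 12, 24 and 36 months. SAP 9.8 says that questionnaire responses will be "summarized by response category (frequency and percent) and by mean (median) response where appropriate" at the same visits. Neither place singles this item out, names its direction, or says whether a mean is appropriate for it.

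Two yes/no items follow in the same block: "Would you recommend the treatment to a friend or relative who suffered from the same nasal symptoms you had" and "If your symptoms were to come back would you chose to undergo the same procedure again".

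**The concern.** A stem and its anchors should describe one construct and run in one direction. Here the stem invites a rating of contentment with the result, where most people would expect a high number to be good. The anchors instead grade residual symptom burden, where a high number is bad. A participant can answer either one in good faith, and the form does not record which was used.

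What is at stake is the label on a reported number. SAP section 2 says results may go into regulatory submissions, study reports and manuscripts. A mean described there as satisfaction, following the wording of SAP 8.4, could name the wrong construct. A reader who assumes that high is good could also take a favourable result for a poor one. The protocol's account of the pivotal trial (section 5.0) makes that assumption natural: its 10-point satisfaction questions had item means of 7.3 to 8.7, with higher values more favourable.

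**Working it through.** The plan gives no figure to reproduce, so the check sets the texts side by side.

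**Construct.** The block heading and the stem ask about satisfaction with symptom relief. Both anchors refer to the effect of symptoms on daily activity, and neither mentions satisfaction.

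**Direction.** Read alone, the stem suggests that 10 is the most satisfied. By the anchors, 1 is the best state and 10 the worst.

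**Is it an artefact of text extraction?** No. The form in Appendix A and the prose of SAP 8.4 show the same mismatch independently.

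**Does the plan resolve it elsewhere?** No. SAP 8.4 repeats the conflict. Table 1 and 9.8 give no scoring direction, recoding rule or label for the item.

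**What a mean would represent under each way of answering:**

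| How participants answered | What the score records | Good end | A mean called satisfaction |
|---|---|---|---|
| All by the anchors | Symptom interference | Low | Wrong label; may be read backwards |
| All by the stem | Satisfaction | High | Right label, but contradicts the printed anchors |
| Some by each | Two constructs on opposed directions | None | Uninterpretable |

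Take two hypothetical participants, both free of symptom effects and both fully satisfied. One follows the anchors and marks 1; the other follows the stem and marks 10. Their mean is (1 + 10) / 2 = 5.5, a mid-scale value that describes neither.

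**Size.** Let q be the share who answered the stem, and g the average gap between their answers and those they would have given on the anchors. The mean then shifts by g × q. The documents give neither quantity. The scale supplies only a ceiling: g cannot exceed 10 − 1 = 9, so each 10% of respondents moves the mean by at most 9 × 0.10 = 0.9 points, and by nothing if g = 0. That limit is a property of a 1–10 scale and is not an estimate for this trial.

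**Standing of the item.** Table 1 places the QoL questionnaire under its own effectiveness objective, separate from the row of other exploratory measures. SAP section 2 notes that the protocol defined no hypothesis tests, while SAP 9.2 applies P < .05 to informational and exploratory analyses. SAP 8.2 makes NOSE the primary assessment of effectiveness, and NOSE does not draw on this item.

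**The case against.** The strongest reply is that the plan already contains most of what a careful report needs. It does not commit to a mean for this item, since Table 1 and 9.8 both limit means to where they are appropriate. Frequencies and percentages by response category are planned, and SAP 8.4 states both anchors. All of this stands, and it is why the point is minor. It does not settle the matter, because the sentence that discloses the anchors also calls the item a satisfaction scale, and nothing tells the analyst that a mean under that name is inappropriate.

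A second reply is that participants probably followed the anchors. The 24 items of the first part run from 0 for no problem to 5 for the worst, and the medication questions start at the much-less-frequent end, so a low-is-better reading fits what comes before. This is fair evidence in favour of the anchors, but it does not exclude answers to the stem. If everyone did follow the anchors, the satisfaction label would be wrong.

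A reader might go further and infer that the item measures interference however it was answered. The documents do not support that: if every participant answered the stem, satisfaction would be the correct label. Nor do they show that any mixing occurred. The pivotal trial's survey ran in the other direction, but it belonged to another study. It explains what a reader may expect of such a score and says nothing about how AERWAY participants answered.

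**Conclusion.** The point holds as an ambiguity in a stated definition. The wording conflict is certain, since it is explicit in two places. Its consequence is conditional on a mean or median being reported for this item and being called satisfaction. In that case the label is wrong if participants followed the anchors, and the number is uninterpretable if some followed the stem. The share who followed the stem, and hence the size of any effect, is unknown and cannot be derived from the documents.

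Severity is minor. One item of the QoL effectiveness objective is affected. The NOSE analyses, the other QoL parts and the two yes/no answers do not depend on it. It would be too strong to conclude that the collected responses are worthless, or that the plan promises a misleading satisfaction claim. The response distribution, shown with its wording, remains reportable, and the plan leaves open whether a mean is given at all.

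**What to change.** In SAP 8.4 and 9.8:

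- State that the stem and anchors of this item conflict, and remove the description of it as a satisfaction scale.
- State that lower is better by the printed anchors, but that some participants may have answered the stem.
- Do not report a mean or median of the item as satisfaction. Present the already planned 1–10 response distribution at each visit, with the stem and both anchors printed beside it.

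An optional descriptive check can use data already collected, since NOSE and the QoL questionnaire are both scheduled at every follow-up visit. Count clearly contradictory responses at each visit: for example, a score at the 10 end with mild NOSE and Yes to both yes/no items, or a score at the 1 end with extreme NOSE and No to both. State that the counts do not correct the item and that mid-scale scores cannot be classified. Simple counts are enough. A full cross-classification would have 10 scores × 5 NOSE rows (four classes plus a score of 0, which lies below the lowest class in SAP 8.2) × 4 yes/no combinations = 200 cells per visit for at most 125 participants, and most would be empty.

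The cost is a few sentences of SAP text and the loss of a single-number satisfaction summary. The form, the data collection and the NOSE analyses do not change.
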